2.2 Intended Use

The Vscan Access Ultrasound system is intended to be used to support diagnostic decision-making when used by trained medical personnel. Personnel operating the devices in this study may or may not have medical training, and results of research scans are not intended for diagnosis. The procedures conducted in this study are intended primarily for research purposes and are not intended as a substitute or replacement for required medical care required outside of this study.

2.3 Comparator/Reference Standard

The comparator/reference standards used for comparison with the investigational product will be the commercially available FHR monitor using the M-mode ultrasound device. All commercially available devices used in this study will be documented on the device listing for the study.

2.4 Concomitant/Ancillary Administrations

2.4.1 Medications and Biologic Products

No medications or biologic products will be administered as part of study procedures.

2.4.2 Laboratory Tests and Sample Processing

No laboratory tests or sample processing is planned as part of the study procedures.

2.5 Accountability

Accurate and adequate records will be maintained for all devices, from time of shipment to the sites until return or disposal of all devices issued by the Sponsor as part of this study, as required by applicable laws and regulations.

GE Healthcare (GEHC) will provide the research Vscan Access R2 Ultrasound with Assisted Fetal Heart Rate Measurement and commercial devices used as the reference standard for study use, which may be used concurrently in other commercial and research activities. Site procedures for verification and documentation of device safety, traceability of software versions, device labeling, and device disposition will be followed. The

Principal Investigator will be ultimately responsible for the security and integrity of research devices at the site during the course of the study.

2.5.1 Issuance

Device will be provided by the Sponsor site. There is no additional calibration or maintenance of study devices planned. The Sponsor may provide maintenance and monitoring of devices as necessary to maintain the integrity of study data.

2.5.2 Disposition

The device(s) will be dispositioned after the study by returning the device to the Sponsor, in accordance with applicable laws and regulations. Identifiable health information will be removed prior to the device disposition.

2.6 Anticipated Risks and Benefits

The device under study has undergone risk assessment, in accordance with International Standards Organization (ISO) 14971, and risks have been mitigated to levels as low as reasonably possible (ALARP).

The risks of study participation are not expected to be greater than those of similar procedures routinely conducted in clinical practice. Post-trial care or follow-up is not required by this study. FHR measurement has been performed for over 20 years and shown to have an excellent safety profile for trained users, because it is non-interventional and does not impact maternal growth or fetal development.

It is also noteworthy that continuous electronic FHR monitoring has been linked to increases in cesarean sections and instrumental births, and therefore costs, without an associated improvement in perinatal outcomes.^{15, 16, 17}

There are no expected risks to subjects, operators, or others in this study beyond those of routine devices in clinical care. Stresses induced on the fetus are minimal and are widely accepted to be well below harmful levels in clinical practice.¹⁸

There are no expected risks to subjects, operators, or others in this study beyond those of similar devices already used in clinical care.

2.6.1 Risk Category and Rationale

The Vscan Access R2 Ultrasound with Assisted Fetal Heart Rate Measurement, as used in this study, is not considered a significant risk device per the 21 CFR §812.3 definition:

- 1) it is not intended as an implant;
- 2) is not purported or represented to be for a use in supporting or sustaining human life;
- 3) is not for a use of substantial importance in diagnosing, curing, mitigating, or treating disease, or otherwise preventing impairment of human health;
- 4) and it does not otherwise present a potential for serious risk to the health, safety, or welfare of a subject.

3. STUDY OBJECTIVES AND ENDPOINTS

3.1 Purpose of the Study

The purpose of the study is to evaluate the procedural accuracy of the Vscan Access R2 Ultrasound System with Assisted FHR feature, versus the use of a conventional FHR monitoring device, such as GE Corometrics* 170 Series Fetal Monitor, for measuring FHR in pregnant women in the 2nd and 3rd trimesters. The Vscan Access R2 Assisted FHR method is an innovative way of assessing FHR that is semi-automated and does not involve any

manual measurements once the fetal heart is scanned, unlike conventional methods of measuring FHR with M-mode ultrasound.

3.1.1 Primary Objective:

- To validate the accuracy of the Vscan Access R2 Ultrasound System Assisted FHR measurement compared to the reference standard in a pregnant population.

3.1.2 Exploratory Objective(s):

- To collect usability data for further user experience optimization.

3.1.3 Safety Objective(s):

- To collect safety information, including type and number of AEs, SAEs, and device issues.

3.2 Study Endpoints

3.2.1 Primary Endpoints:

- FHR data from the investigational and comparator devices on a per-sample basis in bpm (beats per minute)

3.2.2 Exploratory Endpoints:

- The number of subject cases containing scan parameters will be reported and descriptively summarized as necessary to assist in evaluation and optimization of the Vscan Access R2 Ultrasound System.

3.2.3 Safety Endpoints(s):

- Type and number of AEs, SAEs, and device issues.

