
Procedures/ Methods:
	
Subjects in the initial pilot period (Part 1) and validation testing (Part 2) will undergo up to 45 minutes of ultrasound scanning, including up to 8 test scans on the Vscan Access R2 Ultrasound System with Assisted FHR (research device) and a conventional commercially available ultrasound device. Subjects will also undergo routine commercially available noninvasive FHR monitoring as a reference. All procedures will be conducted at a Sponsor, GE Healthcare (GEHC), facility. All members of the study staff will be qualified based on experience and trained prior to participation.
 
The study population will consist of asymptomatic women ages 18 or older in the second (2nd) and third (3rd) trimesters of pregnancy. Users will be instructed to use the VScan Access R2 device to take a 3 second video of the volunteer, which will result in a calculated fetal heart rate measurement from the monitor. Volunteers will also undergo routine commercially available FHR monitoring using the current standard of care.
 
The first session (Part 1) will be a run-in session, in which the parameters and procedures will be a replica of the study but these results will not count towards the documented results. There will be four (4) sessions following this run-in session (Part 2). Each of these sessions will be approximately 3-4 hours in length over a period of 1-2 weeks.
 
In each session, there will be 1-2 users and 3 volunteers. The users will be instructed to take as many measurements as possible during the allotted time. Finalization of the procedure to calculate accuracy is to be determined based on the run-in procedures executed in Part 1. The specific procedures for the measurement of accuracy which will be used for validation will be performed by the team during Part 1 of the study.

Objectives:
	
Data from Part 1 and Part 2 may be pooled or analyzed as separate subgroups, as determined necessary by the sponsor.
 
The primary objective is to validate the accuracy of the VScan Access R2 ultrasound assisted FHR measurement compared to the reference standard in a pregnant population.
 
The exploratory objective is to collect usability data for further user experience optimization.
 
The safety objective is to collect safety information, including type and number of AEs, SAEs, and other device issues.

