3.3 Summary of Study Design

This is a Clinical, pre-market open label, non-randomized, prospective, single-site, non-blinded, research study, that will enroll from the accessible adult (aged >18 years) female population in the 2nd and 3rd trimesters of pregnancy. The study will be conducted in two stages, beginning with a run-in study (Part 1), followed by a clinical study (Part 2). The results of the run-in pilot study will not be included in the results and data analysis; rather, Part 1 of this study will be used to test procedures and determine any experimental factors that have yet to be defined. The study will be conducted at a GE-operated facility. The study is expected to last approximately 6 weeks. The study is not statistically powered for any measure, and is intended to evaluate procedural accuracy of the Vscan Access R2 Ultrasound System Assisted FHR versus use of a conventional FHR monitor (reference): GE Corometrics* 170 Series Fetal Monitor.

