10.8 Statistical Analysis

No statistical hypothesis testing is prospectively planned. Gestational age/number and other variables or subgroups determined necessary by the Sponsor, at its discretion, will be summarized as tables and listings, which may include appropriate descriptive statistics when applicable. Subject disposition and number of image sets collected will be summarized in the final report.

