10.8.1 Interim Analysis

No interim analyses are intended to be conducted as part of this study. The Sponsor may access the study data at any time during the study, as necessary for engineering purposes.

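### The primary objective is to validate accuracy, but the plan defines no paired difference, agreement statistic, acceptance limit or single reference, and does not require these to be fixed in writing before Part 2 data are seen

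*Combined protocol and SAP*

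**What the plan says.** The primary objective in section 3.1.1 reads: "To validate the accuracy of the Vscan Access R2 Ultrasound System Assisted FHR measurement compared to the reference standard in a pregnant population". The purpose statement in 3.1 and the design summary in 3.3 use the softer verb 'evaluate'. The primary endpoint in 3.2.1 is "FHR data from the investigational and comparator devices on a per-sample basis in bpm (beats per minute".

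Sections 10.6 and 10.7 state that no hypothesis is tested and nothing is powered. On analysis, 10.8 says "Gestational age/number and other variables or subgroups determined necessary by the Sponsor, at its discretion, will be summarized as tables and listings", and adds subject disposition and the number of image sets. It does not mention a comparison between devices.

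The accuracy method is deferred. The Synopsis (Procedures/Methods) says "Finalization of the procedure to calculate accuracy is to be determined based on the run-in procedures executed in Part 1", and 3.3 says "Part 1 of this study will be used to test procedures and determine any experimental factors that have yet to be defined". Table 1 in 5.6 describes Part 2 as scanning with fixed parameters. The study is non-blinded (3.3). No interim analysis is intended, but 10.8.1 adds: "The Sponsor may access the study data at any time during the study, as necessary for engineering purposes".

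On Part 1 data, the Synopsis says "Data from Part 1 and Part 2 may be pooled or analyzed as separate subgroups, as determined necessary by the sponsor", whereas 3.3 says "The results of the run-in pilot study will not be included in the results and data analysis", and 5.6 agrees with 3.3.

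**The concern.** A validation claim needs four things: the quantity compared, the device it is compared with, the statistic, and the value of that statistic that counts as success. The endpoint supplies two columns of raw readings and none of the four. Deferring the method to Part 1 would be acceptable if Part 1 had to end in a written, dated procedure, but no section requires one.

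Three features add to the problem. In an open study whose data the sponsor may look at throughout, nothing in the plan prevents the statistic or limit from being chosen after Part 2 readings are known. If Part 1 data may be pooled, the readings that shaped the procedure could also be used to test it. And if the reference is not settled, the comparison could be made against a device other than the monitor named in 3.3. Section 12.6.1 lists regulatory claims among the permitted uses of the data, so the result may be relied on outside engineering.

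**Working it through.** **1. Is an accuracy measure defined anywhere?**

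| Element | What the documents give |
|---|---|
| Paired difference | 5.7 pairs the scans at collection; no section makes the difference the analysis variable |
| Agreement statistic | None in 3.2, 6.6 or 10.8 |
| Acceptance limit | None; the 120 to 160 bpm in 4.1 is a normal FHR range, not a tolerance |
| Repeat pairs per woman | Up to 8 (Synopsis; 5.7 says 8 will be attempted); no method for the clustering |
| Written, dated procedure before Part 2 data are seen | Not required; the blocked schedule in 5.7 covers scan order, and the amendment rule in 9.8 does not mention the accuracy procedure |

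**2. Is there one reference?**

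| Section | Reference |
|---|---|
| Synopsis (Regulatory Status), 3.3, 4.1 | Corometrics 170 Series fetal monitor |
| 3.1 | A conventional monitor, with the Corometrics as an example only |
| 2.3 | An FHR monitor using the M-mode ultrasound device |
| 5.7 | A commercial ultrasound device, labelled the reference standard, used while an FHR monitor is also fitted |
| 6.6 | The CRF takes values from the reference and research ultrasound devices |

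Section 5.7 mentions three instruments and then says that FHR is collected from both devices. Read literally with 6.6, the monitor's reading might not reach the CRF.

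Monitoring and scanning are simultaneous (5.7). However, the Vscan value comes from a 3-second clip (Synopsis) and a pair occupies about 5 minutes (5.7). No rule says which reference reading in that slot is matched to the clip.

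**3. Can the missing rule matter?** The plan has no figure to reproduce: it gives no SD, tolerance, alpha or power. The following is an illustration only. Assumptions: differences normal with zero bias; 15 women (Table 1; 4.2 and 10.7 say 20) with 8 pairs each; intraclass correlation (ICC) 0.3; and one tolerance T applied to all rules. Let r = SD of differences / T.

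- Rule A: mean bias within T.
- Rule B: at least 95% of pairs within T.
- Rule C: both 95% limits of agreement within T, using between- plus within-woman variance.

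The true share of pairs within T is P(|Z| < 1/r), and the true limits lie at ±1.96r × T. The chance of success is from 20,000 simulated studies.

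| r | True share within T | True limits / T | A | B | C |
|---|---|---|---|---|---|
| 0.3 | 99.9% | ±0.59 | 100% | 100% | 100% |
| 0.4 | 98.8% | ±0.78 | 100% | 99.7% | 98% |
| 0.5 | 95.4% | ±0.98 | 100% | 68% | 35% |
| 0.6 | 90.4% | ±1.18 | 100% | 8% | 1% |

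A repeat run gave 69% and 36% at r = 0.5, which is within simulation error. Rule A passes largely by construction. With zero bias, the standard error of the mean at r = 0.5 is 0.5 × √(3.1/120) = 0.08 T, so a failure would need a deviation of about 12 standard errors.

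**4. Why the repeats need a method.** The plan proposes no interval. If one were built for mean bias with the 15 × 8 = 120 pairs treated as independent, the variance would be understated by the design effect 1 + 7 × ICC. True coverage would be about P(|Z| < 1.96/√(design effect)).

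| ICC | Design effect | Effective pairs | 1.96/√(design effect) | Coverage |
|---|---|---|---|---|
| 0.1 | 1.7 | 70.6 | 1.50 | 87% |
| 0.3 | 3.1 | 38.7 | 1.11 | 73% |
| 0.5 | 4.5 | 26.7 | 0.92 | 64% |

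Simulation gave 86.7%, 73.2% and 63.9%. A t interval on the women's means covered about 95% at all three ICC values.

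**The case against.** The strongest reply is that this is an openly descriptive, unpowered study for engineering development (2.1, 3.3, 10.6 to 10.8), that 3.1 and 3.3 say only 'evaluate', and that Part 1 exists to settle the method, with Part 2 then run under fixed parameters. Regulatory claims are one item in a general data-reuse list. Much of this stands: no hypothesis test or larger sample is called for. But a descriptive study must still say what it describes, the stated primary objective is to validate, and fixed scanning parameters are not an agreement statistic.

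Some stronger readings are tempting but not supported:

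- *The sponsor intends to choose the criterion after seeing results.* The documents do not say so, and data access is tied to engineering purposes. The point is only that nothing rules it out.
- *The number of pairs is open-ended, because users are told to take as many measurements as possible.* The Synopsis caps scanning at 8 test scans and 45 minutes, and 5.7 attempts 8 pairs in about 40 minutes. Fewer than 8 pairs is plausible; many more is outside the plan.
- *The operator is not recorded.* Sections 6.6 and 6.7 do not list operator, but the blocked schedule and the exam information in 5.7 may supply it, and the CRF itself is not in the documents.
- *The simulation shows that the verdict turns on the rule.* It uses assumed inputs and one tolerance for three different quantities. The rules agree at a ratio of 0.3 and nearly agree at 0.4.

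**Conclusion.** The concern holds and should be resolved before Part 2 data are seen, because pre-specification cannot be restored afterwards. It rests on the text: a validation objective, an endpoint of raw readings, an analysis section with no device comparison, conflicting descriptions of the reference, and contradictory statements about Part 1 data. Followed as written, the plan gives no defined accuracy result.

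Its numerical size cannot be fixed from the documents. The spread of about 100%, 68% and 35% at an SD-to-tolerance ratio of 0.5 shows only that the choice of rule can matter. It depends on zero bias, 15 women, 8 pairs, ICC 0.3 and a common tolerance. The coverage figures apply only if an interval ignoring clustering were later added.

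**What to change.** Before Part 2 data are seen:

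1. In 3.2.1, define the primary endpoint as the paired difference, Vscan minus one named reference, with a rule for matching the two readings in time. Reconcile the Synopsis, 2.3, 3.1, 3.3, 5.7 and 6.6, and make sure that reference's reading is on the CRF.
2. In 10.8, report mean bias and 95% limits of agreement by a repeated-measures method that accounts for pairs within a woman and allows fewer than 8 pairs. Base no interval on pairs treated as independent. Show results by operator descriptively.
3. State the bpm tolerance and the statistic it applies to, or change 'validate' to 'estimate agreement'.
4. Delete the pooling sentence in the Synopsis, and put the accuracy procedure settled in Part 1 into a dated SAP or amendment.

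Minor and separate: confirm that the CRF captures the actual operator and experience level, and reconcile the 1 to 2 users per session in the Synopsis with the minimum of 2 operators per subject in 5.7.

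The cost is short SAP text and a few CRF fields (operator, level, time stamp, reference reading), with no added subjects or scans. Intervals that respect the clustering will usually be wider, and a stated tolerance is one that the device can fail.

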
Endpoints:
	
The primary endpoint is FHR data from the investigational and comparator devices on a per-sample basis in bpm (beats per minute).
 
The exploratory endpoint is the number of subject cases containing scan parameters will be reported and descriptively summarized as necessary to assist in evaluation of usability of the Vscan Access R2 Ultrasound System.
 
The safety endpoint is the type and number of AEs, SAEs, and device issues.

Eligibility criteria:
	
Inclusion criteria: All included subjects will be:
 
 1. Women aged 18 years or older at the time of consent; 2. By self-report, are in the 2nd or 3rd trimester of pregnancy; 
AND
 
 3. Able and willing to provide written informed consent for participation. 	
Exclusion criteria: Subjects will be excluded that:
 
 1. Are direct employees/contractors of General Electric (GE); 2. Have anatomical characteristics or comorbid medical conditions that prevent completion of ultrasound scanning using the study device; 
OR
 
 3. Are potentially put at additional risk by participating, in the opinion of study staff.

Sample size and Sites:
	
Up to 25 subjects will be included as part of this study to achieve the targeted number of complete and evaluable subjects. The target sample size for this study is 15 subjects. This includes testing up to 5 subjects in Part 1 and 20 subjects in Part 2 of the study. The sample size for both study parts is based on estimation necessary for study device evaluation and validation requirements. This study is not statistically powered for any measure.
	

Study duration:
	
The study is expected to last approximately 6 weeks. Estimated start date: 01/Sep/2017 Estimated end date: 30/Oct/2017
	

ADMINISTRATIVE STRUCTURE OF INVESTIGATION		
Clinical Affairs Project Manager (Sponsor Contact):	[name] Tel: [name] e-mail: [contact]	GE Healthcare (GEHC) Address: [name]
Research Manager:	[name] Tel: [name] e-mail: [contact]	GEHC Address: [name]
Medical Monitor:	[name], DNB, MBBS Tel: [name] e-mail: [contact]	GEHC Address: [name]

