4.2 Number Subjects

Up to 25 subjects will be included as part of this study to achieve the targeted number of complete and evaluable subjects. The target sample size for this study is 15 subjects. This includes testing up to 5 subjects in Part 1 and 20 subjects in Part 2 of the study. The sample size for both study parts is based on estimation necessary for study device evaluation and validation requirements. This study is not statistically powered for any measure.

There is only a single population under study, which is intended to include a range of clinical cases representative of FHR exams conducted at a typical site. This protocol does not prospectively specify any quotas based on scan type or anatomy. However, the site should attempt to enroll a diverse range of subjects including race, ethnicities, and anatomies in order to test a range of features on the study device.

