5.7 Subject Procedure

Subjects will be asked basic demographic and pregnancy status questions. Subjects will be screened for eligibility and no other preparations are required to participate. Following consent, eligible subjects will be fitted with a conventional FHR Monitor while simultaneously undergoing a non-invasive abdominal ultrasound scan using the Vscan Access R2 system with Assisted FHR and a commercially available ultrasound device (reference standard). FHRs will be collected using both devices.

Eight (8) paired ultrasound scans with FHR Monitor determination will be attempted for each subject participating in the study (a total of 16 scans each, 8 with the research device and 8 with the reference device). Each paired scan will last approximately 5 minutes for both determinations, for a total of approximately 40 minutes of total ultrasound exposure. Breaks may be provided between scans based on operator availability or requests by the subject. At least 2 operators will perform scanning for each subject.

A prospective blocked schedule detailing the order in which scanning will be conducted for each operator and subject will be prepared before the start of subject scanning.

Up to 5 clinicians (Experienced sonographers, Novice users e.g. newly qualified sonographers, nurses/midwives, etc.) - with an approximate 80-20 split of novice vs. experienced - with respect to ultrasound familiarity & scanning experience will be aspired for.

The resultant ultrasound and case data (including basic demographics; self-reported pregnancy status; and information about when and how the ultrasound exam was conducted) will be collected for each subject.

All procedures will be conducted at a Sponsor, GE Healthcare (GEHC), facility. All members of the study staff will be qualified based on experience and trained prior to participation.

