6.7 Exploratory Assessments

The device operator will save the ultrasound images, which includes information about the parameter of scanning, for each subject than completes an ultrasound scan in the study. Additional information will be recorded to the CRF as follows:

- Subject ID
- Date of scan
- Duration of scanning
- Patient demographics (age, height, weight, race/ethnicity)
- Gestational age and number, self reported or by LMP or EDD from previous scans
- Trimester (2nd or 3rd)

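### The only exploratory endpoint in effect counts women who completed a scan, so it is nearly insensitive to how usable the device is

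*Combined protocol and SAP*

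**What the plan says.** Section 3.1.2 gives one exploratory objective: "To collect usability data for further user experience optimization". Section 3.2.2 gives one exploratory endpoint: "The number of subject cases containing scan parameters will be reported and descriptively summarized as necessary". The Endpoints row of the synopsis states what the count is for: "to assist in evaluation of usability of the Vscan Access R2 Ultrasound System". Section 3.2.2 itself refers to evaluating and optimising the system and does not use the word usability.

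Section 6.7 says when a woman's record will hold scan settings: "The device operator will save the ultrasound images, which includes information about the parameter of scanning, for each subject than completes an ultrasound scan". Its CRF list also includes "Duration of scanning", next to subject ID, date, demographics, gestational age and number, and trimester. It has no field for the operator, for the outcome of an attempt, or for duration by attempt.

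On the number of scans, section 5.7 says: "Eight (8) paired ultrasound scans with FHR Monitor determination will be attempted for each subject participating in the study". The Procedures/Methods row of the synopsis speaks instead of at most eight test scans, and also of operators taking as many readings as time allows.

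Section 10.8 plans tables and listings, subject disposition and the number of image sets. It names no usability summary.

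**The concern.** An endpoint should vary with the thing it is meant to describe. This one is fixed mainly by how many women are enrolled and scanned. Two devices of very different ease of use could give almost the same count, and section 10.8 already reports disposition and image sets, so the count adds little.

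What is at stake is modest but real. The protocol's rationale is that the workflow helps novices scan efficiently, and Table 1 plans roughly four novice operators to one experienced. Whether novices obtain a reading, and how long they take, is the natural usability question. The visits could answer it descriptively, but no endpoint asks it.

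**Working it through.** The protocol gives no power or precision figure for this endpoint, so there is nothing to reproduce. The check has two steps.

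**1. What the count is.** By section 6.7, saved images carry the settings, and images are saved for each woman who completes a scan. One scan is enough on that wording. The count is therefore the number of women with a completed scan. That is about 15 at target (section 4.2: "The target sample size for this study is 15 subjects"). The ceiling is 20 for Part 2 alone or 5 + 20 = 25 for both parts (section 4.2: "This includes testing up to 5 subjects in Part 1 and 20 subjects in Part 2 of the study"). Table 1 in section 5.6 gives 15 for Part 2. That conflict is a separate matter and does not change this point.

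**2. How far it moves with success per attempt.** Inputs:
- N = 15 women (target) or 20 (Part 2 maximum in section 4.2).
- 8 attempts per woman (section 5.7).
- p = chance that one Vscan attempt succeeds. This is an assumption; the protocol gives no value, so a range is shown.
- Attempts are taken as independent, and a woman is counted once at least one attempt succeeds. Both are assumptions.

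Expected count = N × [1 − (1 − p)^8]. Expected successful scans = N × 8 × p.

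Example, p = 0.3: 0.7^8 = 0.0576, so 1 − 0.0576 = 0.9424. Then 15 × 0.9424 = 14.14 women, and 15 × 8 × 0.3 = 36 scans.

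| Assumed p | Chance of at least one success in 8 | Count, N = 15 | Count, N = 20 | Successful scans, N = 15 (of 120) |
|---|---|---|---|---|
| 0.1 | 0.5695 | 8.54 | 11.39 | 12 |
| 0.3 | 0.9424 | 14.14 | 18.85 | 36 |
| 0.5 | 0.9961 | 14.94 | 19.92 | 60 |
| 0.7 | 0.9999 | 15.00 | 20.00 | 84 |
| 0.9 | 1.0000 | 15.00 | 20.00 | 108 |

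From p = 0.3 to 0.9 successful scans triple, while the count rises by 15.00 − 14.14 = 0.86 of a woman.

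**Sensitivity to the assumptions.** If all eight attempts in a woman succeeded or failed together, the expected count would be N × p (for example 15 × 0.5 = 7.5) and would follow p. Exclusion criterion 2 works against that extreme, because it removes women in whom scanning with the study device cannot be completed. In the other direction, section 6.7 ties image saving to completing a scan and not to obtaining a heart rate. If images are saved without a reading, the count does not depend on p at all.

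**Information available from the same visits.** The synopsis plans four Part 2 sessions with 3 volunteers each, so 4 × 3 = 12 women; section 4.2 allows 20. At eight attempts each this is 12 × 8 = 96 to 20 × 8 = 160 attempts. They are clustered within 12 to 20 women and about five operators, so they are not 96 to 160 independent observations.

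**The case against.** The best defence has four parts.

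- **The objective is only to collect data.** No hypothesis is tested and the study is not powered for anything, so a count of records does show whether collection took place. This stands as far as it goes. But the synopsis assigns the count to evaluating usability, and for that it is weak.
- **The endpoint mentions a descriptive summary, and duration is already recorded.** Section 5.7 also collects information on how the exam was conducted, and section 10.8 lets the sponsor tabulate other variables. This stands in part: a useful ingredient is on the CRF. But no setting, statistic or grouping is named, and duration is not listed by attempt, device or operator. Section 5.7 also plans about 5 minutes for each pair, so total time is partly set by design.
- **Failures could appear elsewhere.** A reader might infer that a device failing in half its attempts would go unnoticed in the study. The documents do not support that. The primary endpoint is per-sample heart rate from both devices, so missing Vscan values might be visible there. Device issues are a safety endpoint, and section 8.7 defines device deficiencies to include malfunctions and use errors. The insensitivity belongs to this count and not to the whole study. Still, no field marks a failed attempt, and the number of attempts is not settled, so failures cannot be reliably recovered by subtraction.
- **The count is not wholly invariant.** This stands: at an assumed success of 0.1 it falls to 8.5 of 15.

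**Conclusion.** The endpoint is poorly matched to its objective and should be changed or supplemented. By section 6.7 it is essentially the number of women who complete a scan. Over an assumed success rate of 0.3 to 0.9 per attempt it moves by less than one woman in 15. That size rests on independent attempts and on one successful scan being enough; strong correlation within a woman would make the count more responsive.

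A reader might go further and conclude that the count says nothing about usability, or that the study cannot meet its exploratory objective. Neither holds: very low success would show in the count, and duration is already collected.

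The point is minor. The endpoint is exploratory and untested, and the primary accuracy result is not affected.

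**What to change.** In section 3.2.2 and the synopsis, replace or supplement the count with:

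- (a) the proportion of attempted Vscan scans that return a heart rate value;
- (b) the duration of each Vscan attempt, with its start and stop points defined and breaks excluded.

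In section 10.8, state that both will be summarised descriptively by operator and by experience level, with attempts treated as clustered within woman and operator. With roughly one experienced operator, the experience effect cannot be separated from that individual, so no formal comparison should be implied.

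Define an attempt, including how a repeated or abandoned one is counted. Reconcile the number of attempts in the synopsis with section 5.7, so that the denominator is fixed.

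Cost: four CRF fields (attempt number, operator ID, success or failure, duration of the attempt) and one table. The blocked schedule already planned in section 5.7 sets the order of scanning by operator and subject and could supply the first two fields. No additional scans, subjects or exposure are needed.
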